## Protocol Title

Balancing Comfort and Clarity with an Adaptive Situation Gain (ASG) Feature in Pediatric Hearing Aid Users

### 1 Background

Children with hearing loss have expressed clear preferences regarding the function of their hearing aids in noise and low-level (quiet) listening environments (Scollie et al., 2010). Generally, environmental noise reduces listening comfort while distance from the talker or low-level conversations reduce listening clarity. Both situations can be addressed with noise management features and remote microphones, however management of the full landscape of listening environments is currently beyond the reach of these technologies. For example, neither feature provides auditory access to low-level input from multiple talkers at a distance which is known to be the source of most vocabulary learning in young children.

Among the hearing-aid prescriptions available to audiologists, two prescriptions are used most frequently with children. The Desired Sensation Level (DSL) prescription (Scollie et al., 2005) emphasizes audibility so that children have as much access as possible to the speech around them. The National Acoustic Laboratory NAL-NL2 prescription (Keidser, Dillon, Flax, Ching, & Brewer, 2011) emphasizes listening comfort. The output prescribed by these two approaches can differ as much as 5 to 15 dB, across frequency. In a field study with grade-school children, DSL (more gain) was preferred when listening to soft or distant speech while NAL (less gain) was preferred when listening to loud speech or in a noisy environment (Scollie et al., 2010a). Put simply, NAL was comfortable but not clear while DSL was clear but not comfortable. The results suggest that the hearing devices used at that time could not accommodate the wide range of input levels experienced by the children and therefore allow the fitting prescriptions to provide listening comfort and clarity.

The opportunity exists to extend the auditory field of children with hearing loss with a soft speech enhancer feature. Specifically, this feature has the potential to improve perception of low-level speech in quiet environments while preventing excessive amplification for louder inputs. Previous studies of adults with hearing loss have suggested a benefit of speech enhancement for perception of low-level speech. It is not uncommon for benefits observed in adults to be the same or larger in children. If so, this feature may provide audiologists with an additional tool to balance clarity and comfort for children. This document refers to this feature as ASG (Adaptive Situation Gain).

### 2 Objectives

The primary objective of this study is to evaluate the contribution of a soft speech enhancer feature (ASG) on auditory perception/memory and listener experience using the amplification strategies that are most common for pediatric fittings (NAL and DSL), in children with mild to moderately-severe sensorineural hearing loss.

There is no secondary objective.

### **3 Description of the investigational device**

The investigational device is a commercially available receiver-in-canal (RIC) hearing aid. Hearing aids are intended to amplify and transmit sound to the ears and to hereby compensate for impaired hearing. The device is worn behind the ear for a duration of up to 16 hours per day, while the receiver is placed in the ear canal up to the ear drum. A qualified hearing care professional programs the device with the aid of Phonak Target to the patient's individual hearing loss.

### **4 Design of the clinical investigation**

This clinical investigation is a single-site, interventional study with a exploratory design. Participants but not experimenters are blinded to the intervention (DSL vs. NAL, ASG on vs. AGS off) as the experimenters are responsible for programming and fitting the study devices. No control group is used for this investigation due to budget limitations.

### **5 Risks and benefits of the investigational device and clinical investigation**

The purpose of this study is to determine if the unique benefits of the NAL and DSL prescriptive algorithms for children with hearing loss can be optimized further with ASG, an adaptive amplification feature designed to improve audibility for speech at low-level input levels.

Previous studies have shown that hearing loss slows the rate of language learning in children, relative to their normal hearing peers (e.g., Blamey et al., 2001). Outcome measures assessing how children with hearing loss perform on tasks involving both familiar and unfamiliar (i.e., new words) were chosen in order to determine if the unique benefits of the NAL (listening comfort) and DSL (speech clarity) prescriptive algorithms can be optimized further with Speech Enhancer for speech at low-level input levels. Optimizing the listening experience of children with hearing loss may support learning by improving audibility for new words as well as familiar ones (particularly when presented at low levels) without exceeding the children's tolerance for high-level input.

Identified risks are no greater than those associated with the participants personal hearing aids.

### **6 Endpoints**

The primary study objective will be assessed by examining listening performance for stimuli presented at low- and high-presentation levels across a broad range of endpoints drawn from three categories of device benefit:

- 1) Familiar words: Perception (word recognition) and memory (familiar word recall)
- 2) New words: Non-word detection, identification, learning, and recall
- 3) User Experience: vocal level, amclusion, and preferred hearing aid settings

### **7 Inclusion and Exclusion Criteria**

Inclusion criteria are as follows:

1. Hearing impaired children between 8 and 15 years of age [Revised: 12 to 17 years of age]
2. Hearing loss is symmetric (no more than a 15 dB difference between the right and left ears at three contiguous frequencies) and mild to moderately-severe in degree (N2-N4 standard audiogram)
3. Oral mode of communication

4. Good written and spoken English language skills
5. Healthy outer ear (confirmed by otoscopy)
6. Informed assent (child) and consent (parent/guardian) as documented by signature

Exclusionary criteria are as follows:

1. Contraindications to the medical device noted upon otoscopy (e.g., ear canal drainage)
2. Known hypersensitivity or allergy to materials of the investigational device or comparator
3. Inability to produce reliable test results
4. Known psychological problems
5. Reported symptoms of vertigo and dizziness by participant

## 8 Measurements and procedures

Study tasks and other relevant measures (audiometry, Real Ear measures) will be completed in the following order:

- 1) Pure-tone audiometry will be completed at the beginning of Session 1, after informed consent/assent has been obtained, in a double-walled, sound-treated booth.
- 2) Real Ear Measurement (REM): Real-Ear Measurement (REM) is a tool used to objectively measure the hearing instrument's frequency response in a participant's ear. In this clinical investigation, on-ear REM will be completed using the Verifit2. Real ear measurement will be completed after hearing aid fitting and before the administration of study tasks.
- 3) After the fitting is complete and while the hearing aids and probe mics are still in the ears (after Real Ear Measures), physical and acoustic occlusion will be measured using the On-Ear Occlusion test option on the Verifit 2.
- 4) Binaural soundfield audiometric thresholds will be obtained but instead of being presented through headphones or insert earphones, tones will be presented through a loudspeaker positioned 1 m away from the participant at 0° azimuth. This will be completed in the hearing aid program with ASG activated. Additionally, a binaural speech reception threshold (SRT) will be obtained in each hearing aid program.

### Nonword Detection Threshold

Speech reception threshold will be obtained. However, instead of only familiar words, participants will be presented with a mix of familiar and unfamiliar two-syllable words and asked to repeat each word they hear. The first words will be presented at a comfortable listening level. If the listener repeats the word correctly, presentation level will be reduced 10 dB and the next word will be presented. If the wrong word is given, presentation level will be increased 5 dB before the next word is presented. This will be continued until the lowest level has been identified corresponding to two out of three correct repetitions. This level is the nonword detection threshold. This task will be completed in each hearing aid program (ASG on, ASG off), and at both test sessions (DSL, NAL).

### Word Recognition

Participants will hear lists of 20 monosyllabic words (10 per presentation level [40 dB, 70 dB], randomized) drawn from the Northwestern University word lists, presented one at a time. The listener will be instructed to repeat each word after they hear it. One 20-word list will be presented in each hearing aid program (ASG on, ASG off). A digital audio recorder (Zoom H2n), placed on the desk between the participant and the loudspeaker, will capture participants' verbal responses, which will be scored offline later by independent examiners. Scores will reflect the proportion of words repeated correctly. This task will be completed at both test sessions (DSL, NAL).

### **Auditory Verbal Learning Task**

Participants will be instructed to listen to a list of 14 words (7 per presentation level [40 dB, 70 dB], randomized) and then repeat as many words aloud as they can remember at the end of the list. After each repetition of the list, the experimenter will select the correctly repeated words using the customized computer software. This will be repeated using the same words four more times, for a total of five trials. This task will be completed in each hearing aid program (ASG on, ASG off), and at both test sessions (DSL, NAL).

### **Nonword Identification**

The nonword identification task will involve a mix of monosyllabic familiar and novel (nonsense) words presented together in three-word phrases. Following the presentation of each phrase, participants will indicate which words (if any) in each phrase were nonsense words by selecting the corresponding numbered button(s) on a computer screen. Visual reinforcement will be provided via an interactive computer game for correct responses, but not for incorrect responses. Performance is represented as the proportion of correct responses for whole phrases or individual words. One list of 20 phrases will be presented in each hearing aid program (ASG on, ASG off). Each list contains five phrases containing 3 real words and 0 nonsense words, five phrases containing 2 real words and 1 nonsense word, five phrases containing 1 real word and 2 nonsense words, and five phrases containing 0 real words and 3 nonsense words. Presentation level (40, 70) will be randomized across phrases. This task will be completed at both test sessions (DSL, NAL).

### **Novel Word Learning**

Participants will learn novel words through a process of trial and error using an interactive computer game. Participants will hear five nonsense words, presented randomly one at a time. Each nonsense word is paired with one of five nonsense objects/characters. A picture of each nonsense image is displayed on one of five buttons arranged across the bottom of a computer screen. Listeners select one of the five images after presentation of each nonsense word. Visual reinforcement for correct selections is provided by a computer game located above the response buttons. The game advances following each correct response (e.g., one piece of a puzzle appears), while no reinforcement is provided for incorrect selections. Participants use the reinforcement to associate each nonsense word with the correct image. Each nonsense word will be presented 20 times (10 per presentation level [40 dB, 70 dB], randomized), for a total of 90 randomized trials. Trial-by-trial performance is calculated in 10 trial bins and fitted with an exponential function to determine the number of trials needed to reach 71%. Overall learning speed is calculated as the number of trials required to reach the criterion level of performance. Fewer trials indicate faster learning. This task will be completed in each hearing aid program (ASG on, ASG off), and at both test sessions (DSL, NAL).

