### **Novel Word Learning Posttest**

Each participant will complete a post-test 1 day after each word-learning session to determine the number of words retained for each hearing aid condition. This task will be conducted remotely. The child will be shown the 10 images learned the day before and a word bank from which to choose the correct response. The word bank will include links to audio files that the child may listen to as they make their decision. The word bank will contain an equal number of target- and nonsense-words. The images learned in the two hearing-aid conditions for the session will be presented randomly one at a time. No feedback is provided for either correct or incorrect responses. Performance is quantified as the number of words correctly identified in each experimental condition (ASG on, ASG off; DSL, NAL).

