## 9 Statistical design and analysis

Datasets to be analyzed, analysis population:

| Outcome Measures  | Fitting Formulas   | Hearing Aid Programs  | Presentation Levels  |
|---|--|---|--|
| 
 
• Ampclusion
 
• Word Recognition
 
• Vocal Level
 
• Familiar Word Recall
 
• Non-word Detection Threshold
 
• Non-word Identification
 
• Rapid Word Learning
 
• Learned Word Recall
 
• Listener Preference
 
 | 
 
• DSL v5a Pediatric
 
• NAL-NL2
 
 | 
 
• Speech Enhancer on at default
 
• Speech Enhancer disabled
 
 | 
 
• 40 dBA
 
• 70 dBA
 
 |

| Outcome Measures  | Fitting Formula  | Hearing Aid Programs  | Presentation Levels  |
|---|--|---|--|
| 
 
• Ampclusion
 
• Word Recognition
 
• Vocal Level
 
• Familiar Word Recall
 
• Non-word Detection Threshold
 
• Non-word Identification
 
• Rapid Word Learning
 
• Learned Word Recall
 
• Listener Preference
 
 | 
 
• DSL v5a Pediatric
 
• NAL-NL2
 
 | 
 
• ASG on at default
 
• ASG disabled
 
 | 
 
• 40 dBA
 
• 70 dBA
 
 |

Primary analysis will compare results of study tasks completed with ASG on compared to ASG off, and with hearing aids programmed using DSL compared to NAL. Where applicable, separate analyses will be completed for each presentation level. The principal investigator (PI) will complete this analysis.

All safety related events will be constantly monitored by the investigators and will immediately reported to the Principal Investigator. Evaluation of any SAE, SADE, or UADE will be conducted promptly using Sonova's standard medical device referral protocol. Confirmed UADEs will be reported to the IRB within 10 days after receiving notice of the event. If it is determined that an event or effect presents an unreasonable risk to subjects, this study, or those parts of the study presenting that risk, will be terminated no later than 5 working days after the determination is made and no later than 15 working days after Sonova USA first received notice of the event.

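### Novel-word learning: the stated 90 trials do not equal 5 words × 20 presentations, and a run that never reaches 71% has no defined score

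*Combined protocol and SAP*

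**What the plan says.** Section 8, Novel Word Learning, sets the task: "Participants will hear five nonsense words, presented randomly one at a time". On its length: "Each nonsense word will be presented 20 times (10 per presentation level [40 dB, 70 dB], randomized), for a total of 90 randomized trials".

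On scoring: "Trial-by-trial performance is calculated in 10 trial bins and fitted with an exponential function to determine the number of trials needed to reach 71" per cent. Then: "Overall learning speed is calculated as the number of trials required to reach the criterion level of performance". The section gives no start value, asymptote or fitting method for the exponential. It does not say whether curves are fitted per presentation level, or what value a run gets if it does not reach the criterion. Each child does the task with ASG on and off at both the DSL and NAL sessions, so there are four runs per child.

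Section 9 lists rapid word learning among nine outcomes and says: "Primary analysis will compare results of study tasks completed with ASG on compared to ASG off", with DSL and NAL compared as well. It adds: "Where applicable, separate analyses will be completed for each presentation level". It names no model and no censoring or missing-data rule.

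**The concern.** There are two linked problems. The run length is inconsistent, so the last observable trial is unknown. And the score exists only if the fitted curve passes 71%. Whether it does depends on an asymptote that the plan leaves open.

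Without a rule, non-attaining runs will be dropped, extrapolated or given a number once the data are in hand. Section 4 leaves the experimenters unblinded, and Section 9 gives the analysis to the principal investigator with no mention of masking. Dropping these runs removes the slowest learners. Half the presentations are at 40 dB, and Section 5 says ASG is meant to improve audibility at low input levels. Runs could therefore be lost unequally between ASG on and ASG off.

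**Working it through.** **1. Trial count.** Inputs from Section 8: 5 words; 20 presentations per word, 10 at each of 2 levels; stated total 90.

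- 5 × 20 = 100, and 5 × 2 × 10 = 100. The stated 90 is not reproduced.
- 90 / 5 = 18 presentations per word (9 per level), or 90 / 20 = 4.5 words. The text supports neither.
- Cross-check on the five words, from the Posttest section: "The child will be shown the 10 images learned the day before". Over two hearing-aid programs per session, that is 10 / 2 = 5 per run.
- In 10-trial bins, 100 trials make 10 bins and 90 make 9. A single level has 50 trials (5 bins) or 45 trials (4.5 bins).

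**2. When the score exists.** The documents give no curve. Assume p(t) = A − (A − 0.20)·exp(−t/τ), with chance 1/5 = 0.20 from the five response buttons. Then t71 = τ·ln[(A − 0.20)/(A − 0.71)].

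- If A ≤ 0.71 there is no solution.
- A = 0.75, τ = 20: 20·ln(0.55/0.04) = 52.4 trials. With τ = 40 it is 104.8, past either stated run length.
- A = 0.80: 20·ln(0.60/0.09) = 37.9 trials at τ = 20, 75.9 at τ = 40 and 113.8 at τ = 60.
- A fixed at 1: t71 = τ·ln(0.80/0.29), which always exists. It falls within 90 trials when the fitted τ is at most 88.7.

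**3. Simulated share of runs not reaching 71% by the last trial.** Correct/incorrect responses were drawn from the assumed curve, and the exponential was fitted by least squares to 10-trial bin means with A free up to 1.

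| True A | τ | Trials | Not reaching 71% |
|---|---|---|---|
| 0.80 | 10 | 90 | about 4% |
| 0.80 | 20 | 90 | about 11% |
| 0.80 | 40 | 90 | about 40% |
| 0.80 | 60 | 90 | about 76% |
| 0.75 | 20 | 90 | about 29% |
| 0.80 | 20 | 50 (one level) | about 36% |

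At τ = 60 the true curve itself crosses only at trial 113.8, so most of that 76% is real non-attainment. At τ = 20 the true curves cross at 37.9 (A = 0.80) and 52.4 (A = 0.75), so the 11% and 29% are fitting noise.

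**4. Free versus fixed asymptote on the same data (90 trials, τ = 20).** With a true ceiling of 70%, about 52% of runs do not reach 71% when A is free, but about 6% when A is fixed at 1. The fixed fit gives a median score of 63 trials (interquartile range 54–73). With a ceiling of 65% the shares are about 74% and 24%.

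**5. Effect of using only scored runs.** Paired simulation: 90 trials, A normal with SD 0.12 capped at 1, τ log-normal with log-SD 0.5, within-child correlation from 0 to 1. The mean difference in complete pairs is expressed as a share of the difference when non-attainers are held at trial 90.

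- ASG moves the mean asymptote from 0.75 to 0.85: 40–62% (7–10 versus 17 trials).
- From 0.90 to 0.95: 47–63% (2.4–3.2 versus about 5 trials).
- ASG changes only τ, from 25 to 15: 81–112%.

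**6. Sensitivity to the value assigned to non-attainers.** Signed-rank test on child-level differences, with 20 children (assumed), correlation 0.5 and mean A 0.85. For the τ-only effect, power is about 70–73% with 91 (last trial + 1) and 55–56% with 200. For an asymptote shift (0.85 versus 0.75) it barely moves: 81% and 79%.

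**The case against.** The study is labelled exploratory, this is one of nine outcomes with none singled out, and Section 9 names no test for any of them. Prescribing a full analysis for this one would go beyond the gap. That stands, and it limits both the weight of the point and how much the fix should dictate. It does not excuse a score that has no value for some runs, or a count that fails simple arithmetic.

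The size also depends on assumed curves. If nearly all children learn quickly to about 90% correct, almost no run is affected (about 0% without a score at A = 0.90, τ = 20). This stands too.

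A reader might infer that a fixed asymptote always hides most non-attainers. It does so at τ = 20 but not generally: at τ = 40 a fixed fit flags about half to three quarters of runs with ceilings of 70% and 65%. A reader might also take last trial + 1 to be an assumption-free worst rank. It is not. Once scores are averaged over formula and differenced within child, the assigned number affects the result, as step 6 shows.

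Finally, pooling the fit over level removes a learning-speed score at 40 dB, although Sections 6 and 9 point to comparisons by level. That is a real cost, and another measure must meet it.

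**Conclusion.** The point holds. The 90/100 contradiction is plain arithmetic, differs by one full bin, and needs no assumption. The documents do not show whether the total or the presentations per word is wrong. The missing asymptote and the missing rule for non-attaining runs are also plain from the text.

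The frequency is unknown. The 4% to 76% range rests on the assumed curve (chance 20%, A = 0.80, 90 trials, free asymptote) and does not predict this trial. A reader might infer that the ASG comparison will be biased. The documents do not support that: understatement is expected only if unscored runs are dropped and ASG acts on the asymptote, and an effect on learning rate alone is distorted little. This should be fixed before analysis. Confidence is high on the gaps and lower on their size.

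**What to change.** 1. Reconcile 90 with 5 × 20 and use the reconciled count as the last trial.
2. State the function, its start value and its asymptote (fixed or estimated). State that it is fitted once per run, pooled over presentation level, because a single level has only 45–50 trials.
3. Keep every run. Treat a run that does not reach 71% by the last trial as right-censored there, and never drop or extrapolate it. Report the number of non-attaining runs per condition. Show that the ASG and formula comparisons do not depend on the value assigned to those runs, for example last trial + 1 against a much larger value.
4. Alongside it, compare proportion correct per run within child, overall and separately at 40 and 70 dB. This score always exists, does not depend on the asymptote, and supplies the by-level comparison that Section 9 calls for.

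Cost: analysis wording and a little more computation; beyond reconciling the count, the task and visits do not change. Trials to 71% would not be reported by level. Noisy fits would give the censored value to some children who truly cross 71% (about 11% of runs at A = 0.80 and 29% at A = 0.75, with τ = 20 and a free asymptote). There would be ties at the last trial, and the result would be a rank comparison rather than a mean number of trials.
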